3. STUDY DESIGN

Purpose and Design

The Cancer Loyalty Card Study (CLOCS) is addressing whether or not data already collected by high street retailers can detect significant changes in purchase behaviours of ovarian cancer patients prior to their diagnosis. We aim to conduct a case-control study of ovarian cancer patients matched with women who do not have ovarian cancer. We will recruit at least 500 recently diagnosed ovarian cancer patients and at least 500 healthy women as controls and collate up to 6 years of prior purchase data.

Recruitment

Women living with ovarian cancer and who own at least one of the participating high street retailer's loyalty cards will be recruited in a clinic by a member of their healthcare team where the study is open (recruitment sites listed in Part C).

Women, 18 years or older, living in the UK who have a loyalty card at the participating high street retailers will be recruited through the study website (www.clocsproject.org.uk) where data collection will be safeguarded using an encrypted web form that includes study consent and the self-report questionnaire. There will be a press release and social media about the study inviting loyalty card holders to visit the CLOCS website for more information and join the study. Any woman considering joining the study can contact the research team using the contact details on the information sheet.

Consent

Ovarian cancer patients will be given the information sheet and consent form in the clinic by a member of their healthcare team. They can take as much time as they need to read through the information sheet. If they choose to participate, they can complete the consent form whenever is convenient for them and return it to the CLOCS team in the freepost envelope provided to them in the clinic.

Alternative recruitment strategy during Covid-19 lockdown to minimise contact with patients

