3.1 STUDY OUTCOME MEASURES

We aim to detect significant changes in purchase behaviours of ovarian cancer patients prior to diagnosis, and potentially improve the sensitivity of detection of cancer “alert symptoms” by stratifying the analysis on risk profiles, cancer stage or histology.

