5.1 RECRUITMENT OF WOMEN WITHOUT OVARIAN CANCER (CONTROLS)

Women without ovarian cancer will be recruited through the study website (www.clocsproject.org.uk) where data collection will be safeguarded using an encrypted web form that includes study consent and the self-report questionnaire. No clinical questionnaire is needed for control participants.

The online participation will take up to 15 minutes and data will be transferred immediately to the secure CLOCS server. The website approach was adopted as one of the outcomes of the proof-of-concept study. It aims to provide a transparent environment where potential participants can make informed decisions about participation in CLOCS, and the data risks are minimised using encryption. We have carefully designed the website to inform the general public about how we will process their data in CLOCS, how they can withdraw from the study if they wish to do so and use it as a platform to provide feedback as we progress in the larger CLOCS project. The research team will use several methods to recruit control participants to the study which will include a press release carried out by the project funders and the Imperial College London public engagement team, dissemination of study flyers and leaflets, and social media marketing techniques on Twitter and Facebook using paid advertisement and unpaid methods. The application of the social media recruitment methods will allow researchers to reach a larger cohort in the UK. The application of both paper-based and online recruitment methods will be carried out throughout CLOCS and will be recorded.

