6. OVARIAN CANCER RISK FACTOR AND SYMPTOM DATA COLLECTION

6.1 Upon choosing to participate in the CLOCS, participants will also complete a questionnaire requesting information about well-established ovarian cancer risk factors and symptoms.

6.1.1 The well-established risk factors include ethnicity, marital status, body mass index, age at menarche, menopausal status, age at menopause, parity,

breastfeeding, hysterectomy, tubal ligation, cancer history, endometriosis, aspirin use, oral contraceptive use, hormone replacement therapy (HRT), family history of ovarian and breast cancers, vaping, and cigarette smoking

- 6.1.2** The questionnaire asks participants about the symptoms experienced (if any) and number of visits to the general practitioner in the year leading up to cancer referral or diagnosis.
- 6.1.3** The questionnaire asks participants about which food and pharmacy stores they shop at regularly, at which stores they own a loyalty card, frequency of use of those loyalty cards, where they heard about the study (for controls only), and the number of people in their household (for adjustment in analysis).
- 6.1.4** In order to understand the impact of COVID-19 on purchase history and ovarian cancer diagnosis delays, the questionnaire includes a question about whether participants have had Covid19 (diagnosed and recovered/diagnosed and still ill/suspected but not formally diagnosed/did not have covid)
- 6.1.5** For participants diagnosed with ovarian cancer (considered cases), this will occur in the clinic or at home if they choose to complete it at home.
- 6.1.6** For participants who do not have ovarian cancer (considered controls), this questionnaire will be completed online.
- 6.2** For participants with ovarian cancer, there will be a separate questionnaire to be completed by their recruiting clinician or member of their healthcare team regarding information about ovarian cancer diagnosis date, type, grade, stage, and surgical outcome, if any. If a patient chooses to complete the questionnaire at home, a member of the clinical care team will send their completed clinical questionnaire with them.
- 6.3** The clinical care teams will not keep a copy of the CLOCS participant consent form.

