9.1.6 Once completed consent forms, risk factor and symptom questionnaires, and clinical questionnaires (for cases) are returned to the CLOCS research team, all information will be entered onto the secure server. The encrypted list of consenting CLOCS participant names and loyalty card numbers for each

participating high street retailer will be transferred to participating high street retailer 1 (HSR1) and participating high street retailer 2 (HSR2) using a secure file exchange provided by Imperial College London. The file transfer will require a password to access what has been transferred. The flow of data is shown in Appendix 2.

HSR1 and HSR2 will never know the cancer status of participants nor their loyalty card status or details at the other HSR.

- 9.1.6a In accordance with the participating high street retailers' policies, healthy volunteers will need to provide a photo ID and utility bill for ID verification. These will be stored in the Secure Enclave, checked, and confirmed to match the details on the consent form. Once confirmed and the high street retailers have returned the purchase history, the photo ID and utility bill be deleted.
- 9.1.6b After two reminders, if we do not receive relevant information to confirm the identity of the participants, we will remove their consent and questionnaire data from our database and permanently delete their responses as they would be considered 'not validated' and we cannot request their data from HSR1 and HSR2.
- 9.1.7 HSR1 and HSR2 will verify participant loyalty card information, and will transfer encrypted participant past purchase data, linked only via the pseudonymised barcode id, back to the CLOCS research team, in line with the data sharing contracts.
- 9.1.8 The CLOCS research team will then save the encrypted participant purchase history data to the CLOCS secure server to be used for analysis.

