9.2 Data analysis

- 9.2.1 The statistical software R will be used for all data analyses.
- 9.2.2 We will define the time prior to diagnosis by which the cases become statistically significantly different in their purchase behaviours to the controls.
- 9.2.3 We will explore this using a multivariable, conditional logistic regression model with ovarian cancer as the outcome and "purchase proportion" at different times prior to diagnosis as the exposure, adjusting for stage and histology and other potentially confounding variables collected from the risk factor questionnaire.
- 9.2.4 We will compare the proportions of purchases in cases to controls, stratified by risk quintiles defined by the epidemiological risk model (estimated n=86 per quintile) or by histology (with expected proportions of high grade serous cases n=335; mucinous cases n=70; endometrioid n=35; clear cell n=35, and low grade serous n=25).
- 9.2.5 We will estimate the predictive values (ROC AUC, PPV, NPV, specificity and sensitivity) of this "early diagnosis" test for each stratum.
- 9.2.6 We will conduct exploratory analyses investigating other methods leveraging the auto correlation in the longitudinal data. Specifically, we will investigate the frequency of purchases and purchase trajectories, to identify purchase patterns (e.g. increasing purchases before diagnosis, purchase peaks, etc.), that are indicative/predictive of the individual disease onset.

- 9.2.7** Using longitudinal approaches, we will investigate if these patterns help in predicting the time-to-onset.
- 9.2.8** This type of approach could be generalised using other purchase categories for further hypothesis generation.

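### Section 9.2.3 adjusts the case-control model for tumour stage and histology, which only cases have, so the model either cannot be fitted or the two terms do nothing

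*Combined protocol and SAP*

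**What the plan says.** Section 9.2.2 restates the primary aim: to find the time before diagnosis at which cases and controls differ in their purchases. Section 9.2.3 gives the only model named for that aim. It is a multivariable conditional logistic regression with ovarian cancer as the outcome and purchase proportion at various times before diagnosis as the exposure, "adjusting for stage and histology and other potentially confounding variables collected from the risk factor questionnaire".

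The data collection sections show where these variables come from:

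- **6.1.1**, the risk factor questionnaire given to all participants, opens its list with "The well-established risk factors include ethnicity, marital status, body mass index, age at menarche" and continues with reproductive, medical, family history and smoking items. Neither stage nor histology is listed.
- **6.2**, for participants with ovarian cancer: "there will be a separate questionnaire to be completed by their recruiting clinician or member of their healthcare team". It covers "information about ovarian cancer diagnosis date, type, grade, stage, and surgical outcome, if any".
- **5.1**, for controls: "No clinical questionnaire is needed for control participants".
- **9.1.6** again ties the form to cases: "clinical questionnaires (for cases) are returned to the CLOCS research team".
- **Section 3**, on design: "We aim to conduct a case-control study of ovarian cancer patients matched with women who do not have ovarian cancer". The ratio and the matching variables are not given.

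Elsewhere the plan uses the tumour variables differently. Section 3.1 speaks of "stratifying the analysis on risk profiles, cancer stage or histology", and 9.2.4 stratifies by histology with expected counts of cases.

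**The concern.** A covariate in a case-control model needs a value in both groups. Stage and histology are features of the tumour. For a woman without ovarian cancer they do not exist, so they are not merely unrecorded. They therefore cannot confound the association between purchases and being a case, and as main effects they are either equivalent to the outcome or carry no information within a matched set.

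An analyst following 9.2.3 literally would reach a model that fails, or one that runs only because the two terms drop out. In the first case the primary-aim model has to be changed after the data are in hand. In the second, the result could be published as adjusted for stage and histology when no such adjustment took place.

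**Working it through.** **Inputs.** 500 cases and 500 controls (Study Summary). Expected histology counts among cases from 9.2.4: high grade serous 335, mucinous 70, endometrioid 35, clear cell 35, low grade serous 25. No stage counts are given, but the algebra for stage is the same.

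**Step 1: who has a histology?** 335 + 70 + 35 + 35 + 25 = 500. This equals the planned number of cases, leaving 0 of 500 controls. Section 6.1.1 lists 18 risk factors, and none is stage or histology.

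**Step 2: the likelihood.** Assume 1:1 sets, since the plan does not state the ratio. Let x be purchase proportion and z the stage and histology indicators, with subscript 1 for the case and 0 for her control. A set contributes

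1 / (1 + exp{−β(x₁ − x₀) − γ′(z₁ − z₀)}).

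Everything turns on z₀, for which the plan gives no value.

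**Step 3: the possible codings of z₀.**

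1. *Controls coded none.* Then z₀ = 0 and every z₁ has a histology indicator equal to 1. Setting all histology coefficients to t and letting t grow sends every contribution to 1. This is complete separation: no finite maximum exists and β is not determined. The same holds in frequency-matched strata, because having a histology is the same as being a case. Separation checks on simulated data found it in 100 of 100 datasets with 1:1 sets, and in 50 of 50 with each of 5, 10 and 20 strata.
2. *Controls missing, complete-case analysis.* All controls drop out. Informative sets: 0 of 500.
3. *Controls given their matched case's value.* This is possible when the cases in a set share the same values, as with one case per set. Then z₁ − z₀ = 0 and γ cancels. Only the purchase variable and the questionnaire covariates remain.
4. *Controls placed at one tumour level.* Sets whose case has another level stop contributing as that level's coefficient diverges. At high grade serous, 500 − 335 = 165 sets are lost and the standard error grows by about √(500/335) = 1.22. At low grade serous, 475 are lost and the factor is √(500/25) = 4.47. The plan does not suggest this coding; it is included only to complete the list.

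**Step 4: numerical check of codings 1 and 3.** One simulated dataset of 500 1:1 sets used the 9.2.4 histology counts. The 0.3 SD purchase shift and the four-level stage distribution are assumptions, not figures from the plan.

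| Coding | Result |
|---|---|
| No stage or histology terms | purchase log-odds ratio 0.299 |
| Matched case's value | 0.299; design rank 1 of 8 columns |
| None | negative log-likelihood 66.1 after 5 iterations, then 0.000004 when the optimiser stopped; purchase coefficient −0.30, 0.31, 0.93 at limits of 5, 20 and 100 iterations |

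The last row shows a model with no finite solution: the purchase coefficient depends on when the software stops.

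**Step 5: what does work.** With histology entered as an interaction with purchase at the matched-set level, the design has full rank (5 of 5). Analysing each case subgroup with its own matched controls is also workable.

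**The case against.** The strongest reply is that the consequence is small. Most of these codings fail at the first fit, any analyst would then drop the terms, and the purchase estimate would be the one intended. That is right, and it is why no hidden bias is claimed. It does not remove the need for a change: the repair would be an unplanned alteration to the primary-aim model, and coding 3 gives no conspicuous failure.

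A second reply is that the authors meant stratification, as in 3.1 and 9.2.4. That is plausible, but 9.2.3 specifies adjustment and sits beside a separate provision for strata. If stratification was meant, the proposed change simply says so.

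Third, 9.2.3 does not call itself the primary model and speaks of exploring the question. It is nevertheless the only model given for 9.2.2, and exploratory work has its own place in 9.2.6.

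Fourth, the reference to the questionnaire in 9.2.3 may apply only to the other confounders, and the list in 6.1.1 may not be exhaustive. Both points are fair. The conclusion does not need that reference, because 4.2, 5.1 and 6.2 already show that the variables exist only in cases.

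**Conclusion.** The concern holds. As main effects in a model for case status, stage and histology cannot be adjusted for. Depending on how controls are coded, the terms separate cases from controls completely, leave 0 of 500 informative sets, or cancel and leave the purchase estimate unchanged. An arbitrary tumour level for controls would discard between 165 and 475 of 500 sets under 1:1 matching.

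Separation under the first coding and the loss of all controls under the second follow from the coding alone, under individual or frequency matching and whatever the effect size. Cancellation requires that the cases in a set share the same values. The set counts and standard error factors for the arbitrary level assume 1:1 sets and the expected histology counts.

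The practical harm is limited to a primary-aim model that cannot be run as specified, or a result wrongly described as adjusted. The questionnaire covariates and the stratified comparison in 9.2.4 are unaffected. It should be corrected before analysis.

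**What to change.** In 9.2.3, delete the five words that put stage and histology in the adjustment list, so that the model adjusts only for potential confounders from the risk factor questionnaire that are measured in both groups. Then add a sentence such as:

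> Stage and histology will not enter the model as main effects. They will be used only to define subgroups of cases, or equivalently as interactions with purchase proportion at the level of the matched set.

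Section 3.1 already provides for stage and histology subgroups, and 9.2.4 for histology.

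It would help to state the matching structure in the same place, because it decides how subgroups are compared. With individual matching and one case per set, each case subgroup is compared with its own matched controls. With frequency matching, each case subgroup is compared with the controls within the matching strata.

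The cost is five words deleted and one or two sentences added before analysis. No new data, recruitment or change in sample size is needed.

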1.2 RATIONALE FOR CURRENT STUDY

Approximately 7,400 new cases of ovarian cancer are diagnosed each year in the UK, and with over 4,000 women dying from the disease each year it is a particularly lethal form of cancer. The symptoms are not well known, are vague and non-specific and most women are diagnosed at a late stage when the cancer has already spread around the peritoneum with poor prognosis. Novel methods are needed to improve earlier detection and thereby improve survival from this disease. We hypothesise that a change in purchasing behaviour, primarily an increase in self-medication to treat these vague cancer symptoms, may provide a novel avenue for earlier diagnosis for cancer.

In this study we propose to use loyalty card data from two participating high street retailers (Boots and Tesco) to investigate purchase behaviour as an opportunity for cancer symptom surveillance. We aim to conduct a case-control study of women with ovarian cancer (cases) matched with women who do not have ovarian cancer (controls) and define the time by which the cases are statistically significantly different in their purchase behaviours leading up to date of diagnosis, compared with the control purchase behaviours.

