- 7.7** The date of recruitment as written on the questionnaire and consent forms will be the final date of purchase data requested by the CLOCS team. At most, up to 6 years of participants' past purchasing data prior to the date of recruitment will be shared with the CLOCS team, depending on the high street retailer's records and when the participant obtained the loyalty card. This includes data about the items purchased (e.g. paracetamol), when (i.e. date of purchase) and where they were purchased (i.e. store postcode). This will not include information on NHS prescriptions or any personally identifiable information, e.g. full name, postcode, ethnicity.
- 7.8** The CLOCS team will save the past purchase data to a secure and encrypted server based at Imperial College London.

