- The user accessing the system is authorised to do what they are attempting to do. That includes searching, updating, deleting and uploading information at the appropriate authorised level for the database(s) or table(s).

In summary, the security architecture provides the optimal level of protection available through implementing best practice network, hardware, software and data security measures.

Participant identity will be linked to the analysis datasets only through a unique barcode assigned when completing the recruitment questionnaire, meaning the data will be pseudonymised. The only identifiable information will be on the consent form along with the participant barcode. Retailer data and questionnaire data will only be linked via the pseudonymised participant barcode. The only person with access to the link between participant identity and the barcode is the chief investigator and this information will be kept in a locked cupboard (paper form) and on the secure encrypted server (electronic form). All researchers on the study team understand all data is confidential.

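### The primary exposure, purchase proportion, has no stated numerator, denominator or product set, and nothing in the plan keeps product classification blind to case status

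*Combined protocol and SAP*

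**What the plan says.** **The exposure.** Section 9.2.3 specifies a conditional logistic regression with "purchase proportion' at different times prior to diagnosis as the exposure". Section 9.2.4 continues: "We will compare the proportions of purchases in cases to controls", stratified by risk quintile or by histology. Section 9.2.5 derives AUC, predictive values, sensitivity and specificity for each stratum. None of these items gives a numerator, a denominator or a product list.

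**What bounds it.** Section 1.1 lists the common symptoms (increased abdominal size, pelvic pain, abdominal pain and bloating, early fullness, difficulty eating) and mentions over-the-counter remedies. Section 1.2 states the hypothesis as "primarily an increase in self-medication to treat these vague cancer symptoms". Section 7.7 describes item-level records: "This includes data about the items purchased (e.g. paracetamol".

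**Main versus other categories.** The Study Summary places other purchase categories among the exploratory analyses, and 9.2.8 says: "This type of approach could be generalised using other purchase categories for further hypothesis generation". The main categories are implied but not listed.

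**Who is masked.** Section 9.1.6 states that "HSR1 and HSR2 will never know the cancer status of participants". Their role in 9.1.7 is: "HSR1 and HSR2 will verify participant loyalty card information, and will transfer encrypted participant past purchase data". Section 10.3 adds: "Retailer data and questionnaire data will only be linked via the pseudonymised participant barcode".

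**The concern.** Someone has to decide which of the many items sold by two retailers count as self-management of ovarian symptoms. That decision creates the exposure. In a case-control study it should be made without knowledge of who is a case, because borderline items can otherwise be kept or dropped according to who bought them.

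The masking in 9.1.6 protects confidentiality at the retailers, who have no stated part in classification. Pseudonymisation hides who a woman is, not whether she is a case. The research team receives the item-level purchases and also holds the questionnaires and the clinical forms for cases.

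Two results depend on this exposure. The primary outcome is a significance statement: the time by which cases differ from controls. The secondary outcome is an alert threshold with predictive values, for which no validation sample is stated. Correcting for the number of time windows would not help, because product choice is a separate source of selection. With the main categories not listed, a reader of the results also could not tell a primary category from an exploratory one.

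**Working it through.** The documents give no alpha, power, effect size or product count for this analysis, so there is no figure of the plan's own to reproduce. The check has two parts.

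**1. Is there a safeguard in the text?**

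| Safeguard | What the documents give |
|---|---|
| Definition of purchase proportion | Name only (9.2.3) |
| Product list or category codes | None; a symptom list (1.1), a general hypothesis (1.2) and one example item (7.7) |
| Date for fixing the list | None |
| Masking to cancer status | Retailers only (9.1.6) |
| Protection of the analysis data | Pseudonymisation (9.1.2, 10.3), which does not conceal case status |
| Boundary between main and exploratory categories | Other categories are exploratory (Study Summary, 9.2.8); the main ones are not listed |

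The contents page lists three appendices: recruitment process, data flow and research sites. None is a product list.

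**2. How much could free choice of product grouping matter?**

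Assumed inputs, none of them from the documents: no true difference; one test per grouping at two-sided 5%; K = 5, 10 or 20 candidate groupings; one time window; correlation between test statistics of 0 or 0.6. Only significant excesses in cases are counted, since 1.2 hypothesises an increase. The nominal rate for one grouping is therefore 5% / 2 = 2.5%.

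Independent groupings: P(at least one case excess) = 1 − 0.975^K.

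- K = 5: 1 − 0.975^5 = 0.119
- K = 10: 1 − 0.975^10 = 0.224
- K = 20: 1 − 0.975^20 = 0.397

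Equicorrelated groupings, ρ = 0.6: P = 1 − ∫ Φ((1.96 − √ρ·u)/√(1−ρ))^K φ(u) du.

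- K = 5: 0.083
- K = 10: 0.126
- K = 20: 0.177

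These figures describe choosing among whole groupings. Choosing single items for one composite is closer to the worry, so a null simulation was also run. It used 500 cases and 500 controls in assumed 1:1 pairs, each product bought by an assumed 20% of women, five products per composite, a paired test at two-sided 5%, and 1,000 runs.

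| Five products taken from 20 candidates | Significant case excess | Mean apparent AUC |
|---|---|---|
| Fixed in advance, independent products | 1.6% | 0.50 |
| Largest case excess, independent products | 83% | 0.55 |
| Fixed in advance, latent correlation 0.3 | 2.8% | 0.50 |
| Largest case excess, latent correlation 0.3 | 48% | 0.53 |

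The rows with the largest case excess represent selection driven wholly by outcome. They are an extreme, not a forecast of what this team would do.

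**The case against.** The strongest reply is that the plan is silent rather than wrong. No section says who will classify items, when, or with which files open. Purchases come back carrying only a barcode, so case status is not on the purchase file and has to be joined to it. Appendix 2, the data-flow summary, was not in the text available for this review, and a masking step there cannot be excluded. Sections 1.1 and 1.2 do bound the field to symptom-related self-medication. Section 9.2.8 openly calls its work hypothesis generation and is not a fault in itself.

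Most of this stands, and it limits what can be claimed. A reader might infer that the team will code products with case status in view. The documents do not say so; they only fail to rule it out. That the team does the coding is itself an inference, drawn from where the item-level data go and from the retailers having no such task.

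A reader might also infer that the apparent lead time would be lengthened. Nothing in the plan or in the calculation above shows that. The calculation covers a single window, and choosing items bought close to diagnosis would mainly strengthen differences near diagnosis.

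A third temptation is to count significance in either direction, which gives 23%, 40% and 64% for independent groupings (1 − 0.95^K). That includes groupings that controls bought more, which is not the hypothesis.

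The reply does not supply a definition of the exposure, a dated product list, or masking of whoever classifies items.

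**Conclusion.** The point holds in a limited form. The primary exposure is undefined, and the available text has no safeguard against its being shaped by case status. If that happened, the case-control difference and the predictive values in 9.2.5 would be biased away from the null. The size is illustrative: roughly 12% to 40% for independent groupings, or 8% to 18% at correlation 0.6, against a nominal 2.5%. It rests on the assumed alpha, number of groupings and correlation. The documents support neither a statement that unmasked coding is planned nor one that lead time would be overstated. This should be changed before purchase data are linked to case status, because a later lock cannot be shown to have been blind.

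**What to change.** 1. In 9.2.3, define the numerator and denominator of purchase proportion. Say whether it is a woman's share of items bought in a window or something else.
2. Before purchases are linked to case status, pool the distinct item descriptions from both retailers and remove barcode, date and store. Have existing team members code each item to categories that follow the symptoms in 1.1 (for example pain, and bloating or eating difficulty) or to not relevant.
3. Lock and date that file, then link.
4. Use only the locked categories in 9.2.2 to 9.2.5, and label any later addition exploratory under 9.2.8.
5. If Appendix 2 already contains a masking step, refer to it in 9.2.3.

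Cost: a few sentences in 9.2, a change in the order of work, and some coding time, which cannot be sized because the documents give no item count. No new data are needed, since the two sources are joined only by barcode (10.3). The downside is that a relevant product missed in the list can enter only as exploratory. The change does not address multiplicity over time windows, which needs its own rule.
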